20.1 Clinical Events Committee

The Clinical Events Committee (CEC) is responsible for the review and final adjudication of adverse events using source documents provided by sites to categorize clinical events and clinical endpoints in the study. The CEC will establish study-related guidelines for the requisite source data and the algorithm followed to classify a clinical event (according to the study definition). The Sponsor will review the definitions prior to the start of the adjudication process.

The CEC will consist of qualified physicians with the appropriate expertise for the type of investigational product or condition under study. The CEC is an independent body, functioning separately from the Sponsor, the investigational sites or anyone otherwise involved in the conduct of the study or the clinical care of study patients. Members will not have any scientific, financial, or other conflict of interest related to the Sponsor or the study Investigators. As appropriate, members of the CEC will be blinded to the primary results of the trial.

The CEC will be responsible for providing adjudication results and minutes of their meetings to the Sponsor for internal review.

The structure and function of the CEC will be documented in the CEC Charter.

20.2 Data and Safety Monitoring Board

The Data and Safety Monitoring Board (DSMB) is a body of professionals (primarily comprised of physicians, a biostatistician, and/or a medical ethicist) which reviews overall study data at intervals pre-determined before the start of the study and/or based on subject enrollment accrual and/or event accrual to assess progress and identify any safety concerns or other issues. The DSMB is independent of the Sponsor, the investigational sites or anyone otherwise involved in the conduct of the study. Members will not have any scientific, financial, or other conflict of interest related to the Sponsor or the study Investigators.

All serious adverse events, device-related complications/malfunctions and events related to the primary safety endpoint will be included in safety reports provided to the DSMB.

Version: 3.0 / 31Jan2023

The DSMB will be responsible for providing to the Sponsor, minutes of their meetings and any recommendations regarding early termination, suspension, or modifications to the study, if the safety and well-being of the patients is in jeopardy.

The structure and function of the DSMB will be documented in the DSMB Charter.

21 Early Termination or Suspension

The Sponsor, DSMB, IRBs, regulatory authorities or the Investigator may choose to temporarily suspend or prematurely terminate the study if the safety and well-being of the patients is in jeopardy.

The Sponsor reserves the right to temporarily suspend or prematurely terminate this study either at a single site, multiple sites or across all sites at any time for reasons including, but not limited to:

- Safety or ethical issues e.g., if in the opinion of the responsible investigator, the incidence and/or severity of adverse events in the study indicates a potential health hazard caused by treatment with the investigational product
- Inaccurate or incomplete reporting of data
- Non-compliance
- Unsatisfactory enrollment with respect to quality or quantity
- Technical reasons (e.g., change in personnel)

If the Sponsor prematurely terminates or suspends the study, they will promptly notify the applicable Investigator(s)/institution(s) and the regulatory authority(ies) of the termination or suspension and the reason(s) for such, in accordance with applicable regulatory requirement(s). The applicable IRB(s)/EC(s) should also be informed and provided with the reason(s) for termination or suspension by the Sponsor or by the Investigator(s)/institution(s), in accordance with applicable regulatory requirement(s). Additionally, in the case of premature termination, the Sponsor will provide direction on the return of all unused investigational product and other study materials. In the case of a temporary suspension at a single site, multiple sites, or across all sites, the Sponsor will ensure all the necessary activities are performed before resuming the study, if approved to continue (e.g., benefit-risk reviewed and remain acceptable or revised).

If the Investigator terminates or suspends the study without prior agreement with the Sponsor, he/she will promptly provide all details to the institution, the Sponsor, and the IRB.

If the IRB terminates or suspends the study, the Investigator will promptly inform the Sponsor with written explanation.

In any case, the investigator(s)/institution(s) must arrange for any continued safety monitoring, treatment and/or follow-up of patients, unless it has been determined by the Investigator that the continued follow-up may jeopardize the rights, safety, and/or welfare of the subject.

Version: 3.0 / 31Jan2023

Subject enrollment may be paused or terminated early if the Sponsor or DSMB determines that the potential benefits of the investigational product/procedure are unlikely to outweigh the risks. For example, if the probability of achieving the target primary endpoint falls below a certain threshold, the trial will be stopped or paused for re-evaluation.

Cordis.

ReliaSeal / P22-8301

Version: 3.0 / 31Jan2023

Appendix A. Definitions

Allergic reaction: The hypersensitive response of the immune system of an allergic individual to a substance.

Asymptomatic: Without symptoms. For example, an asymptomatic infection is an infection with no symptoms.

Blood clot: Blood that has been converted from a liquid to a solid state. Also called a thrombus.

Complication: In medicine, an additional problem that arises following a procedure, treatment or illness and is secondary to it.

Device related complication - complication attributed to the device (e.g., graft migration, graft infection, etc.).

Procedure-related complications - complication not attributed to device but arises following the procedure (e.g., cardiac issue, renal insufficiency, etc.).

Death: All-cause mortality.

Device deficiency: Inadequacy of a medical device with respect to its identity, quality, durability, reliability, safety, or performance. Includes malfunctions, use errors, and inadequate labelling.

Device malfunction: The failure of a device to meet any of its performance specifications or otherwise perform as intended. Performance specifications include all claims made in the IFU/IB.

Dilation: The process of enlargement, stretching, or expansion. The word "dilatation" means the same thing. Both come from the Latin "dilatare" meaning "to enlarge or expand."

Inflammation: A basic way in which the body reacts to infection, irritation or other injury, the key feature being redness, warmth, swelling and pain. Inflammation is now recognized as a type of nonspecific immune response.

Occlusion: A complete absence of flow within a blood vessel.

Peripheral: Situated away from the center, as opposed to centrally located.

Rupture: A break or tear in any organ or soft tissue

Scan: The data or image obtained from the examination of organs or regions of the body by gathering information with a sensing device.

Stroke: Any acute, new, persistent, documented neurological deficit ending in death or lasting greater than 24 hours and classified by a physician as a stroke.

Version: 3.0 / 31Jan2023

Thrombosis – Formation of thrombus within a blood vessel leading to significant limitation of blood flow, requiring secondary intervention to restore blood flow (e.g., thrombolysis, thrombectomy, PTA)

Ultrasound: High-frequency sound waves used to bounce off tissues using special devices. The echoes are then converted into a picture called a sonogram.

Version: 3.0 / 31Jan2023

Appendix B. Acronyms and Abbreviation

Acronym / Abbreviation	Term
ACT	Activated clotting time
AE	Adverse event
AP	Anterior/Posterior
ARF w/ Dialysis	Acute Renal Failure with Dialysis
ARF w/o Dialysis	Acute Renal Failure without Dialysis
atm	Atmospheric pressure
AV	Arterial Venous
BID	Twice Daily
BMI	Body Mass Index
BP	Blood Pressure
BUN	Blood urea nitrogen
CAD	Coronary Artery Disease
CAD	Carotid Artery Disease
CBC	Complete blood count
сс	cubic centimeter
CEC	Clinical Events Committee
CFA	Common Femoral Artery
CFR	Code of Federal Regulations
CHF	Coronary Heart Failure
CI	Confidence Interval
СК	Creatine kinase
CK-MB	Creatine kinase myocardial-band isoenzyme
cm	Centimeter
COPD	Chronic Obstructive Pulmonary Disease
CPK	Creatine Phosphokinase
CRF	Case Report Form
CRO	Contract Research Organization
CSR	Clinical Study Report
СТ	Computerized Axial Tomography Scan
CVA	Cerebrovascular accident
DIC	Disseminated Intravascular Coagulation
dl	deciliter
DM	Data Management
DSMB	Data and Safety Monitoring Board
DUS	Duplex Ultrasound
EC	Ethics Committee
eCRF	Electronic Case Report Form
EDC	Electronic Data Capture
Fr	French (sizing unit for devices)
GCP	Good Clinical Practice
GGE	Generalized Estimating Equation
GI	Gastrointestinal
am	Gram
ЙСТ	Hematocrit
HGB	Hemoglobin
HHS	Health and Human Services (Department of)
HIPAA	Health Insurance Portability and Accountability Act

CONFIDENTIAL

Page 55 of 66

Acronym / Abbreviation	Term
HR	Heart Rate
IB	Investigator Brochure
ICF	Informed Consent Form
ICH	International Council for Harmonization
ICU	Intensive Care Unit
IDE	Investigational Device Exemption
IFU	Instructions for Use
IMA	Inferior Mesenteric Artery
in	Inch
IRB	Institutional Review Board
ITT	Intent-to-treat
IV	Intravenous
IVRS	Interactive Voice Response System
IVUS	Intravascular ultrasound
I PO	Left Posterior Oblique
1/1	Liter
m/Mon	Month
MC	Manual Compression
MedDRA	Medical Dictionary for Regulatory Activities
ma	millioram
MI	Myocardial infarction
mm	Millimeter
mmHa	Millimeters of mercury (unit of pressure)
MHI W	Ministry of Health Labor and Welfare
NSTEMI	Non-ST segment Elevation Myocardial Infarction
NVHA	New York Heart Association
OR	Operation Room
PE	Physical Examination
PLT	Platelet
PMA	Premarket Approval
PMS	Post Marketing Surveillance study
PRN	As Required
RPO	Right Posterior Oblique
PRO	Patient-Reported Outcomes
PT	Prothrombin Time
	Percutaneous transluminal angionlasty
	Partial Thrombonlastin Time
	Perinheral Vascular Disease
	Once Daily
RBC	Bed blood cell
RCT	Randomized Controlled Trial
RVD	Reference vessel diameter
SAE	Serious adverse event
	Standard deviation
SD	Superior Meconteric Artery
	Superior Mesellenic Artery
	Therasic Aartic Anourusm
	Transient Ischemic Attack
	Tansient Isonennic Allduk
	rarger resion(s) revascularization

Acronym / Abbreviation	Term
TTA	Time to Ambulation
TTDE	Time to Discharge Eligibility
TTH	Time to Hemostasis
UADE	Unanticipated Adverse Device Effect
UBD	Use by date
ULN	Upper Limit of Normal
US/USA	United States/United States of America
USFDA	United States Food and Drug Administration
VCD	Vascular Closure Device
VO	Volume obstruction
WBC	White blood cell
WHO	World Health Organization
WNL	Within Normal Limit

Cordis

ReliaSeal / P22-8301

Version: 3.0 / 31Jan2023

UADE	Unanticipated Adverse Device Effect
ULN	Upper Limit of Normal
UNL	Upper Normal Levels
US/USA	United States/ United States of America

TABLE OF CONTENTS

10 INTERIM ANALYSIS	
11 HANDLING OF MISSING DATA	

1 INTRODUCTION

This document outlines the detailed statistical analysis methods to provide the appropriate clinical information on "A Multicenter, Prospective, Randomized, Controlled, Open Label Trial To Evaluate The Safety And Efficacy Of MYNX Control[™] Venous Vascular Closure Device 6F-12F Vs. Manual Compression In Patients Who Have Undergone Endovascular Procedures Utilizing Up To 12F Procedural Sheaths."

Note: The MYNX Grip VCD is indicated for use to seal femoral arterial and femoral venous access sites while reducing times to hemostasis and ambulation in patients who have undergone diagnostic or interventional endovascular procedures utilizing a 5F, 6F or 7F procedural sheath.

2 STUDY OBJECTIVE

The primary objective of this study is to demonstrate safety and efficacy of the MYNX CONTROL[™] Venous Vascular Closure Device 6F-12F vs. manual compression in sealing femoral venous access sites in patients who have undergone endovascular procedures utilizing one or more procedural sheaths up to 12F.

3 STUDY DESIGN

This study is a multicenter, prospective, randomized, controlled, open label clinical study to enroll 204 subjects with an additional group of subjects to be part of the initial roll-in phase. The number of roll-in patients will be determined based on physician training and usability. All subjects who sign the informed consent and are randomized to either treatment arm will be followed through 30 days post procedure. There will be approximately 15 participating study sites all located in the United States.

Of the 204 subjects targeted for enrollment, 72 (48 MYNX CONTROL[™], 24 Manual Compression) will be enrolled in the duplex ultrasound (DUS) sub-study (see section 8.7). In the event that the full 72 subjects are not consented for the DUS sub-study by the time the targeted 204 subjects are enrolled, enrollment will continue beyond the targeted 204 subject until 72 subject have consented to participate in the DUS study.

4 ENDPOINTS

4.1 Safety Endpoint

The primary safety endpoint is defined as the rate of combined major venous access site closure-related complications through 30 days post procedure, attributed directly to VCD or manual compression without other likely cause.

- Access site-related bleeding requiring transfusion, surgical intervention, or rehospitalization
- Vascular injury requiring surgical repair

- Access site-related infection confirmed by culture and sensitivity, requiring intravenous antibiotics and/or extended hospitalization
- New onset, permanent (i.e., persisting at 30-day follow-up) access site-related nerve injury
- New onset access site-related nerve injury requiring surgical repair
- Pulmonary embolism requiring surgical or endovascular intervention and/or resulting in death, to be confirmed by CT pulmonary angiography, lung ventilation/perfusion scan (VQ scan), or autopsy
- Pulmonary embolism not requiring surgical or endovascular intervention and/or not resulting in death, to be confirmed by CT pulmonary angiography or lung ventilation/perfusion scan (VQ scan)

4.2 Effectiveness Endpoints

The co-primary efficacy endpoints Time to Ambulation (TTA) and Time to Hemostasis (TTH) as defined below:

- **Time to Ambulation (TTA)**-Defined as time (in hours) between removal of the final VCD (treatment arm) or of the final sheath (control arm) and when subject stands and walks 20 feet without evidence of rebleeding from any femoral venous access site.
- **Time to Hemostasis (TTH)**-Defined as time (in minutes) between removal of each VCD (treatment arm) or of each sheath (control arm) and first observed and confirmed venous hemostasis per access site.

5 SAMPLE SIZE

All sample sizes were calculated assuming a 2:1 ratio of MYNX CONTROL[™] VCD to manual compression.

Time to Ambulation:

Time to ambulation is a co-primary endpoint for effectiveness. The Type 1 error for this calculation was set at 0.025 for a one-sided test. Assuming that the treatment group ambulates in 3.0 hours on average and the control group ambulates in 6.0 hours and both groups have a standard deviation of 6.0 hours, then an effective sample size of 192 subjects provides 90% power to detect this difference in time to ambulation between the two groups of subjects. Adjusting for a missing data rate of 5%, total enrollment is 204 subjects.

Time to Hemostasis:

Time to hemostasis is a co-primary endpoint for effectiveness. The Type 1 error for this calculation was set at 0.025 for a one-sided test. A generalized linear mixed model will be used to compare the MYNX CONTROL[™] Venous VCD device with manual

compression (control). Initial estimates of the average time to hemostasis were taken from historical MYNX family devices and compared to manual compression. Previous MYNX family studies only studied one access site per subject within the femoral artery. The observed average time to hemostasis as well as the standard deviations of those measurements helped inform the design of this trial where the standard deviation would be used as an estimate of subject-to-subject variation. For the sample size calculation, it is assumed that each subject has 3 access sites in the femoral vein. These access sites will be closed with either the MYNX CONTROL[™] Venous VCD device or manual compression. Only one method of closure will be used per subject. Time to hemostasis will be measured for each access site separately.

It is assumed that hemostasis times are log-normally distributed. Using previous study data where time to hemostasis averaged 6 minutes for the MYNX CONTROLTM Venous VCD device and 13 minutes for manual compression, estimates of μ and σ of the lognormal distribution were obtained and used in the calculation of sample size for this endpoint.

A generalized linear mixed model is used with the subject as a random effect. The specific model used is:

$$y_{ijk} = \mu + \tau_i + S_{j(i)} + e_{k(ij)}$$

where τ_i is the treatment effect and S_{ij} is the random effect of subject within treatment. e_{ijk} is the unexplained variation in the model. Further, it is assumed that:

$$y_{ijk} \sim N(\mu_{ij}, \sigma^2)$$

 $S_{j(i)} \sim N(0, \sigma_S^2)$

and

 $e_{k(ij)} \sim N(0, \sigma_e^2)$

To adjust for the correlation in hemostasis time between the access sites within subject it is assumed that the correlation structure is compound symmetric. A sample size of 150 subjects (100 MYNX CONTROL[™] VCD and 50 manual compression) will provide approximately 95% power to detect a difference in hemostasis times of 7 minutes between MYNX CONTROL[™] VCD and manual compression. Note that these calculations were made in the log transformed space to assess power. Also, the variation between access sites within subject was estimated at approximately half of the variation observed between subjects.

Major Complication Rate:

The rate of combined major venous access site closure-related complications through 30 days post procedure, attributed directly to VCD or manual compression without other likely cause is the primary safety endpoint. The one-sided Type I error was set to 0.025 for the purpose of sample size calculation. The safety endpoint will be analyzed using a non-inferiority approach on a per limb basis. For the purposes of sample size

calculation, both groups are assumed to have a 1.5% major complication rate. The non-inferiority window has been established at 5 percentage points.

Within-subject correlation can affect the power of the study depending on the degree of correlation. However, the degree of correlation within-subject due to potentially multiple limbs is unknown and there is not robust and relevant data on which to base any associated assumption. Since this is unknown, conservatively sample size is calculated assuming only one limb per subject, or in other words, the number of subjects in the study assuming independence between subjects. Calculations for a two-sample test of binomial proportions for a Z test under a normal approximation show a sample size of 204 subjects should provide approximately 80% power for this endpoint. To the extent that some subjects will contribute multiple limbs to the actual analysis, the power would be higher than that from calculations based only on the numbers of independent subjects. Though missing data for the primary safety endpoint is unlikely, the additional data contributed by multiple limbs will help offset any power loss due to missing data.

Time to Discharge Eligibility (secondary endpoint):

Initial estimates for time to discharge eligibility were obtained from the VASCADE MVP Venous Vascular Closure System (Cardiva Medical Inc.) Summary of Safety and Effectiveness Data. The average time to discharge eligibility for VASCADE MVP Venous Vascular Closure System (Cardiva Medical Inc.) was 3.1±1.3 hours and for manual compression it was 6.5±1.9 hours. For sample size calculation, the Type 1 error rate was set to 0.025. A sample size of 23 subjects provides more than 95% power to demonstrate that the average time to discharge eligibility is significantly less for the MYNX CONTROL[™] Venous group relative to manual compression.

Study Sample Size:

The sample size for adequate power on the primary safety endpoint was the largest and will be used as the overall sample size for this trial.

The study also incorporates a DUS sub study with enrollment target of 72 randomized subjects. This substudy is not powered and does not impact the primary statistical design and the main analytical cohort of the first 204 subjects that are randomized .

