16.4 Statistical Hypotheses for Endpoints

Primary Effectiveness Endpoint- Primary efficacy will be measured using co-primary endpoints consisting of Time to Ambulation (TTA) and Time to Hemostasis (TTH) as defined below:

• **Time to Ambulation (TTA)**-Defined as elapsed time (in hours) between removal of the final VCD (device group) or of the final sheath (control group) and when subject stands and walks 20 feet without evidence of rebleeding from any femoral venous access site.

The null and alternative hypotheses of the primary effectiveness comparison for TTA are given below

Ho: $\mu_{Mynx \ Control} \geq \mu_{manual \ compression}$

Ha: $\mu_{Mynx \ Control} < \mu_{manual \ compression}$

Where μ_x is the average time to ambulation for the specified group

• Time to **Hemostasis (TTH)**- Defined as elapsed time (in minutes) between removal of each VCD (device group) or of each sheath (control group) and first observed and confirmed venous hemostasis (per access site analysis)

The null and alternative hypotheses of the primary effectiveness comparison for TTH are given below:

Ho: $\mu_{manual \ compression} - \mu_{Mynx \ Control} \leq 5$

Ha: $\mu_{manual \ compression} - \mu_{MynxControl} > 5$

Where μ_{xx} is the mean time to hemostasis for the indicated group and 5 minutes is the superiority margin.

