A generalized linear mixed model is used with the subject as a random effect. To adjust for the correlation in hemostasis time between the access sites within subject, it is assumed that the correlation structure is compound symmetric. The Type I error rate was set to a one-sided 0.025 (or equivalently, a two-sided 0.05 level) for the purposes of sample size calculation. A sample size of 150 patients (100 MYNX CONTROL[™] Venous VCD and 50 manual compression) will provide approximately 95% power to detect a difference in hemostasis times of seven (7) minutes between MYNX CONTROL[™] Venous VCD and manual compression. Note that these calculations were made in the log transformed space to assess power. Also, the variation between access sites within patients was estimated as approximately half of the variation observed between patients.

The specific model used is:

 $y_{ijk} = \mu + \tau_i + S_{j(i)} + e_{k(ij)}$

where τ_i is the treatment effect and S_{ij} is the random effect of subject within treatment. e_{ijk} is the unexplained variation in the model. Further, it is assumed that:

$$y_{ijk} \sim N(\mu_{ij}, \sigma^2)$$

 $S_{j(i)} \sim N(0, \sigma_S^2)$

and

 $e_{k(ij)} \sim N(0, \sigma_e^2)$

TTH Assumptions	
Power	~95%
Alpha	1-sided 0.025
Allocation	2:1 VCD:MC
VCD mean	6
MC mean	13
Standard Deviation	Determined in the log transformed space
Attrition correction	5%

Version: 3.0 / 31Jan2023

Total Sample Size 150 patients

Sample Size for Primary Safety Endpoint: The primary safety endpoint of major venous access site closure-related complications through 30 days post-procedure, attributed directly to VCD or manual compression without other likely causes will be analyzed using a non-inferiority approach based on a generalized estimating equation (GEE) approach for logistic regression, using a working compound-symmetric covariance structure. This method would account for potential within subject correlation. We will perform the test at the one-sided 0.025 alpha level. For the purposes of sample size calculation, both groups are assumed to have a 1.5% major complication rate. The non-inferiority window has been established at 5 percentage points.

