8.5 Analyses of Effectiveness Endpoints

8.5.1 Primary Effectiveness Endpoint Analysis

There are two co-primary effectiveness endpoints: Time to hemostasis, and time to ambulation.

The average time to ambulation in each treatment group will be compared using a standard T-test. The test will be done on a per subject basis. The null and alternative hypotheses are:

Ho: $\mu_{Mynx \ Control} \geq \mu_{manual \ compression}$

Ha: $\mu_{Mynx \ Control} < \mu_{manual \ compression}$

where μ_x is the average time to ambulation for the specified group. A p-value for this one-sided test less than 0.025 will indicate that the time to ambulation for the subjects using the MYNX CONTROLTM Venous VCD was significantly less than for those where manual compression was used.

The average time to hemostasis will be analyzed on an access site level. The null and alternative hypotheses of the primary effectiveness comparison for TTH are given below:

Ho: $\mu_{manual \ compression} - \mu_{Mynx \ Control} \le 5$ Ha: $\mu_{manual \ compression} - \mu_{Mynx \ Control} > 5$

where μ_x is the mean time to hemostasis for the indicated group and 5 minutes is superiority margin.

The average time to hemostasis will be analyzed using a generalized linear mixed model where subject is considered a random effect with multiple access sites and treatment group is a fixed effect. The times to hemostasis in the manual compression group will be reduced by 5 minutes to account for the hypothesis that the time to hemostasis for the MYNX CONTROL[™] Venous VCD device is at least 5 minutes less than manual compression. The analysis will consist of testing the coefficient on the fixed effect for treatment group. If that coefficient is found to be significantly different from zero, then the direction will be evaluated to assure that the hemostasis time is reduced on average when using MYNX CONTROL[™] Venous VCD. This test is by default a two-sided test, so a p-value of 0.05 or less with the direction of the difference showing shorter times for MYNX

CONTROL[™] Venous VCD will correspond to a one-sided test at the 0.025 level results in achieving this endpoint.

If the distribution assumptions (normality, lognormality) for the primary effectiveness endpoints do not hold based on Shapiro-Wilk test at the 0.05 alpha level, a non-parametric Wilcoxon rank sum test will be used to compare the treatment groups.

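### The stated 95% power for time to hemostasis names a 7-minute difference but neither the 5-minute margin nor an SD, so it is not shown to apply to the shifted test that decides the endpoint

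*SAP*

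**What the plan says.** SAP section 5 and Protocol 16.8 give the TTH sample size in nearly the same terms. The SAP takes mean times of 6 minutes for the device "and 13 minutes for manual compression, estimates of μ and σ of the lognormal distribution were obtained". It assumes 3 access sites per subject and takes the variation between sites within a subject as about half of that between subjects. It concludes that 150 subjects (100 device, 50 MC) "will provide approximately 95% power to detect a difference in hemostasis times of 7 minutes", and the Protocol likewise states "approximately 95% power to detect a difference in hemostasis times of seven (7) minutes". Both say the calculation was done after log transformation, at one-sided 0.025. The SD row of the Protocol's TTH table says only that the value was worked out on the log scale. No number appears in either document.

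The hypothesis is set elsewhere. In Protocol 16.4 the null is that MC minus device is at most 5, and "5 minutes is the superiority margin". SAP 8.5.1 explains how this is tested: "The times to hemostasis in the manual compression group will be reduced by 5 minutes", and the treatment coefficient of the mixed model is then compared with zero. If a Shapiro-Wilk test rejects the distributional assumption (normality or lognormality), a Wilcoxon rank sum test replaces the model. Under Protocol 16.9.1, trial success needs TTH, time to ambulation and the safety endpoint all to be met.

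**The concern.** At the planning means, the shifted test has to detect 8 versus 6, a gap of 2 minutes. The power sentence names 7 minutes and is silent on the margin. A reader cannot tell whether the 95% is power against a null of zero or a null of 5 and, with no SD given, cannot work it out.

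The log scale adds a second difficulty. A margin in minutes does not carry over simply to logs: once 5 minutes is taken from lognormal times, the result is no longer lognormal with the same log-SD, and some values fall to zero or below. Even a calculation that did include the margin may therefore not describe the planned test. TTH is required for trial success, so low power here directly raises the chance that the trial fails on this endpoint.

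**Working it through.** **Inputs from the documents.** Means 6 and 13; margin 5; 100:50 for the TTH calculation and 136:68 enrolled; one-sided 0.025; stated power about 95%; 3 sites per subject; within-subject variation about half of between-subject variation (read here as variances).

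**Not in the documents.** Any SD for TTH. The stated 95% therefore cannot be reproduced. It can only be inverted, to find the SD that it implies.

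**Step 1: implied SD on the log scale.** With between-subject log-SD s, the standard error of the difference in subject means is

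SE = s × √[(1 + 0.5/3)(1/100 + 1/50)] = s × √0.035 = 0.1871 s.

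Power of 95% needs the log difference to equal (1.960 + 1.645) × SE = 0.6744 s.

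- Margin ignored: ln(13/6) = 0.773, so s = 0.773/0.6744 = 1.15.
- Margin used as 8 versus 6: ln(8/6) = 0.288, so s = 0.288/0.6744 = 0.43.

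**Step 2: margin ignored, s = 1.146.** Power for 8 versus 6, still treating the shifted times as lognormal with the same log-SD:

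- 100:50: SE = 0.2144; Φ(0.2877/0.2144 − 1.96) = Φ(−0.62) = 27%.
- 136:68: SE = 1.146 × √[1.1667 × (1/136 + 1/68)] = 0.1838; Φ(0.2877/0.1838 − 1.96) = Φ(−0.39) = 35%.

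**Step 3: margin used as ln(8/6), s = 0.427.** The closed form gives 95% at 150 by construction and about 99% at 204. It assumes that the shifted MC times are lognormal with the device arm's log-SD, which they are not. The per-site log variance is 1.5 × 0.427² = 0.2735 (SD 0.523), so the MC log-mean is ln 13 − 0.137 = 2.428. The share of MC site times at or below 5 minutes is Φ((1.609 − 2.428)/0.523) = Φ(−1.57), about 6%. After the shift these have no logarithm, and the documents do not say how they would be handled.

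**Step 4: simulate the shifted test.** Lognormal times with means 6 and 13, a common log-SD, 3 sites per subject and within-variance half of between; 5 minutes subtracted from each MC time; pooled t-test on subject means in minutes. Ranges cover separate simulation runs.

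| Between-subject log-SD (assumed) | Log-scale formula, 8 v 6: N=150 / 204 | Simulated, in minutes: N=150 / 204 |
|---|---|---|
| 0.30 | over 99% / over 99% | 95-96% / 99% |
| 0.43 | 95% / 99% | 71-72% / 83-84% |
| 0.50 | 87% / 95% | 58% / 68% |
| 0.60 | 73% / 85% | 42-43% / 53-54% |

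At 0.43 the rank sum test gives about 33% at 150 and 42% at 204. The reason shows in the medians. The site-level medians are 13 × e^(−0.137) − 5 = 6.3 minutes for shifted MC and 6 × e^(−0.137) = 5.2 for the device, a gap of 1.1 minutes rather than the 2 minutes between the means.

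**The case against.** The strongest reply is that a power statement names the assumed true difference and the null is set elsewhere. Protocol 16.4 states the null of 5 minutes ahead of the sample-size section, so 95% power for 7 minutes is compatible with testing against 5. This stands. A reader might infer that the margin was left out, or that the 95% is an arithmetic error. The documents do not say so, and without an SD no miscalculation can be shown.

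The benign branch is also at least as plausible. Ignoring the margin requires a between-subject coefficient of variation near 165% (log-SD 1.15), whereas using it requires about 45% (log-SD 0.43). The observed discharge-eligibility figures in SAP section 5 have coefficients of variation of 42% (1.3/3.1) and 29% (1.9/6.5). The ambulation planning SD of 6 hours on means of 3 and 6 hours is far larger, so this does not settle the matter, but the 27% and 35% should be read as one end of a range.

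It is tempting to say that the stated power holds only for a very small SD. On the log scale that the plan says it used, the limit is about 0.43 at 150 and about 0.50 at 204, which is not extreme. The limit becomes restrictive only for an analysis in minutes. SAP 8.5.1 does not fix the scale, since it mentions both normality and lognormality and allows a switch to Wilcoxon, so the simulated t-test is one reading of the plan.

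Finally, TTH did not set the sample size (150 against 204). Low power would cost the sponsor a missed endpoint and would not create a false success. What survives is that the sentence does not describe the deciding test, cannot be checked, and is not delivered at N=150 for an analysis in minutes by either closed-form log calculation.

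**Conclusion.** The concern holds in conditional form, as something that should be fixed. The 95% is not tied to the 5-minute null and rests on an undisclosed SD. Depending on how it was obtained, power for 8 versus 6 is about 27% at 150 and 35% at 204 (margin ignored, log-scale approximation), or about 72% and 83-84% (margin entered as ln(8/6), data analysed in minutes), with less under the Wilcoxon fallback. It is about 95% at 150 in minutes only if the between-subject log-SD is about 0.30 or less. A simulation that applied the shift correctly with an SD of that size would support the stated figure; the documents neither show nor exclude this.

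These results assume lognormal times with a common log-SD in both arms, 3 sites for every subject and the half-variance reading of the within-subject statement. The hypothesis, margin and decision rule agree across the two documents and are not in question, and nothing here shows that 204 subjects are too few.

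**What to change.** In SAP section 5 and Protocol 16.8, replace the sentence with the power of the planned test: null difference at most 5 minutes, true means 6 and 13, 5 minutes subtracted from each MC time, obtained by simulation on the scale on which the data will be analysed. State:

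- that scale, and how shifted times at or below zero are handled if it is the log scale;
- the between-subject log-SD from the prior studies;
- the assumed within-subject variation (about half of between) and 3 sites per subject. The within-subject part has to remain an assumption, because SAP section 5 says the earlier studies had one access site per subject;
- a short table of power over a range of SDs at 150 and at 204 less 5% (204 × 0.95 = 193.8, about 194 subjects), with the Wilcoxon fallback alongside.

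Keep 95% only if that calculation supports it. The cost is one rerun with inputs the plan says were already estimated, and one paragraph in each document. The stated power may turn out lower. No change to enrolment, endpoint or test is asked for.
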